- a Evaluation assessments should be performed prior to administration of IMP unless otherwise indicated. Results should be reviewed by the Investigator prior to the administration of the next dose. All visits should occur within 3 days of scheduled visit unless otherwise noted.
- b Screening must occur within 28 days of dosing. The following procedures must be repeated at the day 1 visit: Medical and cancer history, physical examination, weight measurement, vital signs, hematology (see h), serum chemistry panel (see h). Lab values must still meet eligibility criteria on cycle 1, day 1. Tumor assessments must be repeated at the baseline visit only if determined to be changed by clinical exam or other clinical observations. SOC procedures performed prior to consent but within the protocol defined screening window for each assessment can be used for study purposes. All research only procedures must be performed after the consent date.
- c Patients may continue with daily dosing of enzalutamide with or without taselisib in the absence of unacceptable toxicities after C2 (or if the toxicity has resolved) and with no clinical evidence of disease progression.
- d The 30-day follow-up assessments should be done 30 (±3 days) days after the last dose of enzalutamide and taselisib. 30 day follow-up can be done by phone or by a clinic visit. Any ongoing toxicities should be documented. Any ongoing serious adverse events will be followed every 3 months until resolution. Any AEs or SAEs considered possibly or probably related to IMP that have not stabilized, returned to baseline, or are considered irreversible will continue to be monitored as per the protocol in Section 7.
- e MRI should be completed only if CT is unclear and a lesion can only be followed on MRI imaging. The CT scan should be completed with contrast. This is considered a research procedure if the patient does not have any signs or symptoms of brain metastases. If the patient must undergo brain imaging for the sole purpose of screening for this study, it is expected that a CT of the head will be done.
- f The physical examination will include measurements of height and weight at screening. Weight will be measured on day 1 of each cycle and at the End-of-treatment visit. Physical examination will include examination of major body systems including neurologic, cardiac, respiratory, gastrointestinal, and skin. Clinically relevant signs and symptoms will be reported as AEs.

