- l Tumor assessment should be performed approximately every 2 cycles (up to -5 days) while on study treatment and at End-of-treatment visit if not obtained within the past 6 weeks. Scans should consist of CT scan of the chest, abdomen, and pelvis and a bone scan at baseline. Subsequent scans should consist of CT chest, abdomen and pelvis, and bone scan if bone metastases were present on the baseline studies. At the end of treatment, all scans (baseline and through disease progression) should be sent on a CD to the Vanderbilt Cancer Imaging Support Laboratory for central review and assessment. See Section 10.5 for details and address.
- m Archived tumor biopsy specimen: 20 unstained slides of archived biopsy block (unstained slides) or fresh tumor biopsy will be requested at the time of enrollment prior to initiation of treatment.
- n Tumor biopsies will only be performed in the phase II portion. A tumor biopsy from a metastatic site will be obtained from patients prior to day 1, at cycle 2 day 14-21, and upon progression of disease. The third biopsy (at the end of treatment) will not be required for patients who are removed from study for reasons other than disease progression. A patient who undergoes a research biopsy procedure for the purpose of this protocol, and in whom inadequate tissue is obtained, is not obligated to undergo a repeat biopsy.
- o See section 9.1. Required only for patients at Vanderbilt and only in the phase II portion. This should be performed prior to tumor biopsy, if possible. If MRI sub-study is not feasible due to scheduling, MRI weight limits, etc., patients may still continue with the remainder of the study.
- p Subjects on the enzalutamide + taselisib arm should begin enzalutamide on day 1 of cycle 1, and taselisib on day 1 of cycle 2.
- q Pill Diary can be found in the packet of supplemental forms.
- r See Section 6.4.2.
- s Phase II only. Biopsy questionnaire should be filled out by the patient on C3D1. Form can be found in the packet of supplemental forms.
- t The cycle 2 day 8 visit is only needed for patients on the combination of taselisib + enzalutamide. Patients on enzalutamide only do not need a visit on this day.

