- 4.1.11** Phase II only: Biopsy of a metastatic lesion in patients with reasonably accessible metastatic lesions (chest wall, skin, subcutaneous tissue, lymph nodes, skin, breast, bones, lung, and liver metastases). If a reasonably accessible metastatic lesion is not available, the patient may go on study provided that archived tissue is available. However, if a reasonably accessible site is available for biopsy, the patient must agree to biopsy. Any patients not undergoing biopsy must be approved for study enrollment by the Protocol Chair. Biopsies may be done with local anesthesia or intravenous conscious sedation, according to institutional guidelines. If a biopsy requires general anesthesia, then it is only allowed if acquisition of tissue is clinically indicated, and excess tissue may be collected for research purposes. Patients without sites available for biopsy must have available tissue [archived formalin-fixed paraffin embedded blocks (FFPB) or fresh frozen tissue from original diagnosis or metastatic setting] for correlative studies per Section 9.2.

Tissue needs to be located and available at the time of registration (tissue needs to be submitted within 3 weeks of study initiation).

**4.1.12** Patients must have adequate hematologic, hepatic, and renal function. All tests must be obtained within 28 days of starting treatment. Labs are to be repeated on C1D1 and must still meet eligibility. These include:

- ANC  $\geq 1500/\text{mm}^3$
- Platelet count  $\geq 75,000/\text{mm}^3$
- HgB  $\geq 9$  g/dL
- Creatinine  $\leq 1.5X$  upper limits of normal (ULN)
- INR  $\leq 2$
- Total serum bilirubin  $\leq 1.5$  x ULN (in patients with known Gilbert Syndrome, a total bilirubin  $\leq 3.0$  x ULN, with direct bilirubin  $\leq 1.5$  x ULN)
- AST and ALT  $\leq 3$  x ULN (or  $\leq 5.0$  x ULN if hepatic metastases are present)
- For patients without known Type II diabetes, the following is required at screening:
  - Fasting plasma glucose  $\leq 160$  mg/dL (7.49 mmol/L) and glycosylated hemoglobin (HbA1c)  $< 7.5$  % or International Federation of Clinical Chemistry (IFCC)  $< 53$  mmol/mol
- For patients with Type II diabetes receiving only oral anti-hyperglycemic therapy (patients receiving insulin are not eligible), the following are required at screening:
  - HbA1c  $< 8.5$  % or IFCC  $< 69.4$  mmol/mol
  - Stable regimen of oral anti-hyperglycemic therapy without insulin usage for at least 3 weeks prior to first study treatment

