### 6.3.1 Taselisib

Taselisib tablets are administered once daily until disease progression or intolerable toxicity. Taselisib administration will begin on C2D1 for patients enrolled on the combination arm (with enzalutamide alone beginning on C1D1). Each dose should be taken with a minimum of 3–4 ounces (90–120 mL) of water with or without food in the morning (before noon). If a dose is missed (not taken by noon), the patient will resume dosing with the next scheduled dose. Missed or vomited doses will not be made up. The occurrence and frequency of any vomiting during a treatment cycle must be noted as an adverse event. Patients should swallow the capsules as a whole and not chew or crush them.

A sufficient number of taselisib tablets should be provided to the patient to last until the next cycle. Patients will be instructed to bring their bottles of study drug and their medication diary with them to each study visit.

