## 6.6 Cross-over post-progression

Patients who are randomized to enzalutamide alone can crossover to receive enzalutamide + taselisib upon disease progression. Patients who are randomized to enzalutamide alone and who discontinue enzalutamide for toxicity cannot crossover to receive single agent taselisib. However, patients on the enzalutamide + taselisib arm can continue to receive single agent taselisib if they discontinue enzalutamide due to toxicity. Patients who cross over to receive taselisib in combination with enzalutamide will follow the assessments and procedures as outlined in the study calendar. The duration of each cycle will continue to be 28 days and the cycle numbers will "reset" to 1 and will be followed by the "X" suffix (e.g., Cycles 1X, 2X, etc.). Crossover therapy (taselisib) must begin no later than 21 days after the clinic visit at which progression is determined, but can begin as early as C1XD1.

Patients must have labs and procedures performed as outlined in the cross-over study calendar and must meet the values as described in the Inclusion Criteria, prior to receiving taselisib based on assessments and procedures performed within 28 days prior to Day 1 of Cycle 1X. Labs and procedures not included in the cross-over study calendar do not have to be repeated. Patients must also agree to a tumor biopsy, as outlined in the eligibility criteria, prior to initiating taselisib. Patients will receive crossover treatment until progression, intolerable toxicity, or elective withdrawal from the study. Patients who crossover will be evaluated with radiologic assessments every 2 cycles until disease progression.

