#### 7.2.1.5 Liver Toxicity

If clinical symptoms or signs suggestive of liver dysfunction occur (e.g., nausea, vomiting, abdominal pain, fatigue, anorexia, “flu-like” symptoms, dark urine, jaundice, or right upper quadrant tenderness), the serum transaminases should be measured immediately. Elevations above baseline should prompt an evaluation should occur to determine the cause of the elevation, including progressive disease and hepatotoxicity from concurrent medications.

If transaminases (ALT/AST) are elevated  $> 3X$  ULN and are thought to be secondary to disease progression, a CT scan should be obtained to confirm disease progression and the patient should be removed from study. If transaminases (ALT/AST) are elevated  $> 3X$  ULN and not thought to be secondary to disease progression, treatment should be withheld until levels fall to  $\leq 3X$  normal levels. If a patient has known liver metastases and baseline transaminases were 3-5X ULN, treatment should be held until levels fall to less than or equal to baseline levels. If total bilirubin is elevated  $> 1.5$  x normal level, treatment should be withheld until level falls to  $\leq 1.5$  x normal levels. If alkaline phosphatase is elevated  $> 2.5$  x normal value, treatment should be withheld until levels fall to  $\leq 2.5$  x normal level (unless bone metastases are present in the absence of liver metastases). A dose reduction should then be administered following resolution of any or all of these liver enzyme abnormalities.

If transaminases are subsequently elevated  $> 3X$  ULN or, if total bilirubin is elevated  $> 1.5X$  normal value, or if alkaline phosphatase is elevated  $> 2.5$  x normal value (unless bone metastases are present in the absence of liver metastases), treatment will again be withheld until AST/ALT decrease to  $\leq 3X$  normal, total bilirubin decreases to  $\leq 1.5$  x normal value and alkaline phosphatase decreases to  $\leq 2.5$  x normal value. A second dose reduction should then be administered. If a patient has known liver metastases and baseline transaminases were 3-5X ULN, treatment should be held until levels fall to less than or equal to baseline levels. For any hepatic toxicity CTCAE Grade 4, or CTCAE Grade 3 that does not resolve within 7 days to CTCAE Grade  $\leq 1$  (or CTCAE Grade  $\leq 2$  if liver infiltration with tumor present), an abdominal CT scan should be performed to assess if it is related to disease progression.

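### Patients with known Gilbert syndrome may enter at total bilirubin up to 3.0 x ULN, but 7.2.1.5 holds treatment above 1.5 x normal with no Gilbert or baseline exception

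*Combined protocol and SAP*

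**What the plan says.** **Entry.** Section 4.1.12 requires total bilirubin of at most 1.5 x ULN, with one exception: "in patients with known Gilbert Syndrome, a total bilirubin" of up to 3.0 x ULN is accepted if direct bilirubin is at most 1.5 x ULN. The Study Calendar (footnote b) repeats the test: "Lab values must still meet eligibility criteria on cycle 1, day 1". For crossover, section 6.6 uses the same limits; patients "must meet the values as described in the Inclusion Criteria, prior to receiving taselisib".

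**Start of taselisib.** Section 6.3.1: "Taselisib administration will begin on C2D1 for patients enrolled on the combination arm". Study Calendar footnote t adds a check one week later: "The cycle 2 day 8 visit is only needed for patients on the combination of taselisib + enzalutamide".

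**Hold and release.** In the first-event paragraph of 7.2.1.5, when total bilirubin is above 1.5 "x normal level, treatment should be withheld until level falls to" 1.5 x normal or lower. After that, "A dose reduction should then be administered following resolution of any or all of these liver enzyme abnormalities". The repeat-event paragraph uses the same bilirubin limits and ends: "A second dose reduction should then be administered". The closing sentence of 7.2.1.5 takes a patient off study, with the value reported as an unacceptable toxicity, if bilirubin is still raised after two reductions.

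**Consequences.** Section 7.2 discontinues a patient whose dose is delayed by more than 28 days. Section 6.9 lets a patient with toxicity from one drug continue on the other. Table 2 gives taselisib 4 mg, then 2 mg, then discontinuation.

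**The concern.** The trial decided to admit Gilbert patients with a raised total bilirubin and protected that decision with a limit on direct bilirubin. The treatment rule does not carry the decision forward. A value that met the entry criterion also triggers the hold, and a patient whose usual level is above 1.5 x ULN has no way to satisfy the release condition.

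Such a patient, randomised to the combination or crossing over to it, could lose taselisib for a laboratory value that the protocol had already accepted. Sites that notice the problem may resolve it differently, because the only relief is discretionary.

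**Working it through.** No figure in the plan needs reproducing; the check compares thresholds, then works out timing and likely numbers.

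**1. Entry limits against hold limits**

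| Test | Entry limit (4.1.12) | Hold (7.2.1.5) | Exception in 7.2.1.5 |
|---|---|---|---|
| AST/ALT | 3 x ULN | above 3 x ULN | – |
| AST/ALT, liver metastases | 5 x ULN | above 3 x ULN | baseline 3–5 x ULN: release at baseline |
| Total bilirubin | 1.5 x ULN | above 1.5 x normal | – |
| Total bilirubin, known Gilbert | 3.0 x ULN, direct at most 1.5 x ULN | above 1.5 x normal | none |
| Alkaline phosphatase | none listed | above 2.5 x normal | bone without liver metastases |

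Reading normal as ULN, the Gilbert entry limit is 3.0 / 1.5 = 2.0 times the hold limit. The conflict covers total bilirubin above 1.5 and up to 3.0 x ULN with direct bilirubin at most 1.5 x ULN.

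**2. Search for an exception elsewhere.** Table 3 has no hepatic row. The phase Ib DLT table (6.2.2) recognises a raised baseline bilirubin, but only to classify DLTs in a phase that is complete. The baseline wording in 7.3.2 concerns enzalutamide toxicities of grade 3 or higher. Neither lifts the 7.2.1.5 hold.

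**3. Timing for a stable patient, read as a taselisib rule because it sits in 7.2.** With 28-day cycles, C2D1 is day 29 and C2D8 is day 36. C2D8 applies if the rule is taken to operate only after a first taselisib dose. The 28-day allowance ends on day 29 + 28 = 57 or 36 + 28 = 64, so it is passed on day 58 or day 65. Both precede the 16-week point, 16 x 7 = day 112.

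**4. A patient fluctuating around 1.5 x ULN.** Each resolved hold requires a reduction: 4 mg to 2 mg, then discontinuation. There is one exception. Where both drugs were held, 7.2 allows taselisib to return to its original dose after 28 days if tolerated. After such a re-escalation, the next reduction is again 4 mg to 2 mg.

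**5. Likely numbers.** Section 15.3 plans 37 combination patients and up to 12 on enzalutamide alone. Section 7.2.1.3 reports 8 combination patients treated before the enzalutamide lead-in was added. At most 37 − 8 = 29 combination patients are therefore still to start under the current schedule, or 29 + 12 = 41 if every enzalutamide-arm patient crosses over. Both are upper bounds: 7.2.1.3 shows that some crossovers had already happened, and 15.4 counts phase I patients at the recommended dose among the phase II evaluable patients.

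The documents give no frequency for this bilirubin range. For an assumed share p of 0.5% to 3%, the expected number is n x p and the chance of at least one is 1 − (1 − p)^n:

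| n | Expected number | Chance of at least one |
|---|---|---|
| 29 | 0.15 to 0.87 | 1 − 0.995^29 = 14% to 1 − 0.97^29 = 59% |
| 41 | 0.21 to 1.23 | 1 − 0.995^41 = 19% to 1 − 0.97^41 = 71% |

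**The case against.** The best defence is section 7.4. Its first bullet lets the treating investigator continue at full dose when a toxicity is judged unlikely to become serious, without asking the Protocol Chair. A stable, pre-existing Gilbert value is a fair candidate. Section 11.2.1 also counts an abnormal laboratory value as an adverse event only if it causes symptoms or leads to treatment or further tests. The coordinating centre reviews eligibility documents before registration (5.4), so a known case could be settled in advance. This stands as far as it goes: relief is available. It remains discretion rather than a rule, and the hold itself is tied to a multiple of normal, not to judgement.

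Three stronger inferences are tempting, and the documents do not support them.

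- *Two crossings of 1.5 x ULN always exhaust taselisib.* Not where both drugs were held and the dose was restored under 7.2.
- *A stable Gilbert patient will be removed and reported as an unacceptable toxicity.* That sentence requires two dose reductions, and reductions follow resolution. A patient who never resolves accrues none, so only a fluctuating patient could reach it.
- *The conflict endangers patients or undermines the two-stage design.* The rule errs towards withholding drug, and no sample size, error rate or decision boundary depends on it.

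**Conclusion.** The inconsistency is in the text and has no standing exception. Followed as written, it keeps taselisib from a Gilbert patient stable above 1.5 x ULN whom the trial chose to admit, ending in discontinuation or enzalutamide alone unless relief is given. A fluctuating patient loses dose levels, subject to the re-escalation provision. The pattern in the table suggests an omission: the liver-metastasis allowance for transaminases is carried from entry into the hold rule, and the Gilbert allowance is not.

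The practical effect is small: probably no more than about one patient, on an assumed frequency. The conclusion rests on reading normal as ULN, the natural reading. It merits correction because the rule gives the wrong instruction and the repair is cheap, not because the trial's conclusions are at risk.

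**What to change.** In both hold paragraphs of 7.2.1.5 add: *For patients with known Gilbert syndrome and baseline total bilirubin >1.5 x ULN, treatment is held for bilirubin only if total bilirubin is >3.0 x ULN or direct bilirubin is >1.5 x ULN, and is released when both are back within these limits.* In the closing removal sentence, state that persistent elevation is judged against the same limits for these patients.

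The baseline condition matters. Without it, a Gilbert patient who starts with normal bilirubin could rise to 3.0 x ULN with no hold. Gilbert patients who start at or below 1.5 x ULN stay under the general rule, and 7.4 remains available for those who drift just above it.

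The cost is one sentence in two paragraphs and one qualifier, in an amendment. Direct bilirubin can be run on the chemistry sample already drawn; Study Calendar footnote h allows additional tests when clinically appropriate, so no visit or blood draw is added. The downside is a higher total-bilirubin stop for these few patients, covered by the direct-bilirubin limit and the unchanged AST/ALT hold above 3 x ULN.

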### 6.2 Phase Ib component of the trial

The phase Ib component is complete. The primary objective of this portion of the trial was to determine the safety profile [dose-limiting toxicities (DLTs) during the first cycle of treatment, and maximum tolerated dose (MTD)] of the combination of taselisib and enzalutamide. The phase Ib portion allowed patients who are estrogen and/or progesterone receptor positive or negative, provided they are HER2 negative (see eligibility criterion 4.1.5).

- Enzalutamide + taselisib: the taselisib dose will start at 2 mg (dose level 1). Dose escalation proceeded among cohorts of 3 patients according to a standard 3+3 algorithm beginning at the lowest dose level.

In addition, pharmacokinetic (PK) sampling was collected from patients enrolled into the Phase Ib part of the study to allow for comparison within the study and to previous observations when taselisib was administered as a single agent in the Phase Ia trials. All open sites were able to participate in the phase Ib component.

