Hepatic	
 
Total bilirubin CTCAE Grade 2 for > 7 consecutive days, if less normal-grade 1 at baseline
 
Total bilirubin CTCAE Grade <math>\geq</math> 3, if grade 2 at baseline
 
AST or ALT CTCAE Grade <math>\geq</math> 2 in conjunction with blood bilirubin d CTCAE Grade <math>\geq</math> 2 of any duration
 
AST or ALT CTCAE Grade 3 for > 7 consecutive days
 
AST or ALT CTCAE Grade 4
 
Serum alkaline phosphatase CTCAE Grade 4
 
Serum lipase and/or serum amylase (asymptomatic) CTCAE Grade 3 for > 7 consecutive days
 
Serum lipase and/or serum amylase (asymptomatic) CTCAE Grade 4
 
ALT or AST of 3X ULN and concomitant bilirubin of >2 X ULN (Hy's Law) with no other explanation other than study drug should be permanently discontinued from treatment with study drug.
 
	
Both taselisib and enzalutamide should be held.
 
If total bilirubin <math>\geq</math> 2 x ULN or <math>\geq</math> CTCAE grade 3 AST/ALT has been demonstrated, these parameters must be repeated at least twice a week until resolution to <math>\leq</math> CTCAE grade 1 (or <math>\leq</math> grade 2 for AST or ALT, if liver metastasis are present) to allow for initiation of re-treatment, and then at least weekly until either resolution or until stabilization.
 
Patients with total bilirubin > ULN (any duration) should have fractionation of bilirubin into total/direct or indirect/direct components and any additional work-up as clinically indicated by these results. Follow-up of hyperbilirubinemia should proceed as per the guidelines above, irrespective of the results of fractionation.
 
For any hepatic toxicity CTCAE Grade 4, or CTCAE Grade 3 that does not resolve within 7 days to CTCAE Grade <math>\leq</math> 1 (or CTCAE Grade <math>\leq</math> 2 if liver infiltration with tumor present), an abdominal CT scan should be performed to assess if it is related to disease progression.

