The following were instructions for DLTs in the phase Ib. Patients who meet DLT criteria must stop taselisib. Patients who meet DLT criteria for hepatotoxicity should hold both taselisib and enzalutamide. Patients whose treatment is interrupted or permanently discontinued due to an adverse event or clinically significant laboratory value must be followed as outlined in the table above, at least once a week for 4 weeks, and subsequently at 4-week intervals, until resolution or stabilization of the event, whichever comes first. Patients that require a dose delay of  $> 28$  days due to a cause unrelated to study participation will have the opportunity to continue study if deemed appropriate to do so by the Protocol Chair of the study. If patients experience a DLT considered related to taselisib, the patient may remain on enzalutamide on-study after resolution of the DLT at the discretion of the treating physician after receiving counseling about alternate treatment options. If patients experience a DLT considered related to enzalutamide, they have the option of remaining on single agent GDC0032 on-study at the discretion of the treating physician after receiving counseling about alternative treatment options. After resolution of the DLT, patients may be able to restart taselisib or enzalutamide at a lower dose at the discretion of the treating physician. However, such cases will be considered a DLT for the purposes of defining the MTD. All patients who continue taking taselisib and/or enzalutamide as a single agent will not be evaluable.

Patients who withdraw or are withdrawn from the study prior to completing the DLT assessment window for any reason other than a DLT or miss  $\geq 7$  days for non-drug related AEs will be replaced. This includes patients whose disease progresses within 30 days of starting the study. Patients requiring dose reduction of enzalutamide or taselisib for reasons other than a DLT in cycle 1 of the phase Ib portion will not be included in the DLT evaluation. After the MTD is reached,

patients in the phase Ib on lower dose levels can dose escalate to the MTD at the discretion of the treating physician and after discussion with the Protocol Chair.

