## 7.2 Taselisib

See Table 3 at the end of this section for taselisib dose modification criteria

Patients who experience an SAE or whose treatment is interrupted or permanently discontinued due to an adverse event or clinically significant laboratory value must be followed as outlined in Table 3 below, at least once a week for 4 weeks, and subsequently at 4-week intervals, until resolution or stabilization of the event, whichever comes first. If a patient requires a dose delay of > 28 days from the intended day of the next scheduled dose, then the patient should be discontinued from the study. All patients must be followed for adverse events and serious adverse events for 30 days following the last dose of taselisib. This can be done as either an in-office visit or by phone. If the taselisib dose is reduced due to an adverse event which is later determined to be secondary to enzalutamide and enzalutamide is discontinued, taselisib can be re-escalated at the discretion of the treating physician after consultation with the Protocol Chair. If both taselisib and enzalutamide are held for an adverse event, enzalutamide should be restarted at the original dose. Taselisib should be restarted at one dose lower than the last dose. After 28 days, if the patient is tolerating both medications well, taselisib may be increased back to the original dose.

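### The permanent stop for combined transaminase and bilirubin elevation (Hy's Law) appears only in the phase Ib DLT table; Section 7, which governs phase II and crossover, directs a restart at a reduced dose instead

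*Combined protocol and SAP*

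**What the plan says.** The protocol has two sets of liver rules.

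- **Phase Ib (Section 6.2.2, Table 1, hepatic row).** A patient with ALT or AST of 3 × ULN and concomitant bilirubin above 2 × ULN, labelled Hy's Law, "with no other explanation other than study drug should be permanently discontinued from treatment with study drug". Table 1 defines dose-limiting toxicities in cycle 1 of phase Ib. Section 6.2 states "The phase Ib component is complete", and the text after the table opens with "The following were instructions for DLTs in the phase Ib".
- **Phase II and crossover (Section 7).** Table 2 starts from the phase II dose of taselisib, 4 mg, with 2 mg as the first reduction and discontinuation as the second. Section 7.2.1.5 sets separate hold limits: transaminases above 3 × ULN if not thought due to progression, bilirubin above 1.5 × normal, and alkaline phosphatase above 2.5 × normal. After the hold: "A dose reduction should then be administered following resolution of any or all of these liver enzyme abnormalities". Where both drugs were held for an adverse event, Section 7.2 adds that "enzalutamide should be restarted at the original dose" and that taselisib restarts one level lower. It continues: "After 28 days, if the patient is tolerating both medications well, taselisib may be increased back to the original dose".

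Table 3, which lists taselisib dose modifications, has no hepatic row. Its catch-all row for other clinically significant toxicities restarts taselisib one level lower after grade 3 and stops it permanently at grade 4.

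**The concern.** Table 1 gives one clear instruction for this event: no more study drug. The text now in force gives another: wait for the values to fall, then restart at a lower dose. The restart sentence covers abnormalities occurring together as well as singly, so the gap is not just silence. A site that follows Section 7 is told to re-expose a patient whom the protocol's own phase Ib rule would have stopped for good. What is at stake is the safety of that patient. Sample size, error rates and the clinical benefit rate are not involved.

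**Working it through.** No figure in the plan needs reproducing. The check follows one patient through both sets of rules.

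1. **Where the stop is stated.** It is in Table 1, hepatic row, and nowhere else. Sections 6.6, 6.9 and 7.1 to 7.4, all rows of Table 3, and the study calendar footnotes contain no rule that combines transaminases with bilirubin.

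2. **Does every patient who meets the Table 1 rule enter the Section 7.2.1.5 hold?** Table 1 needs bilirubin above 2.0 × ULN. Section 7.2.1.5 holds above 1.5 × normal. Taking normal as ULN (an assumption), 2.0 / 1.5 = 1.33, so the hold limit is always crossed. This is so even if ALT is exactly 3 × ULN and does not exceed the transaminase limit.

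3. **What follows.** For illustration, assume a first event on 4 mg with ALT 4 × ULN and bilirubin 2.5 × ULN, not due to progression and below grade 4.

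| Rule | Action once values resolve | Taselisib dose |
|---|---|---|
| Table 1 (phase Ib) | Permanent stop | 0 mg |
| Section 7.2.1.5 with Table 2 | Restart one level lower when ALT is at most 3 × and bilirubin at most 1.5 × | 2 mg (2/4 = 50%) |
| Table 3 catch-all, if grade 3 | Restart one level lower after recovery to grade 1 or better | 2 mg (50%) |
| Section 7.2, if both drugs were held | Return to starting dose permitted after 28 days of good tolerance | 4 mg (4/4 = 100%) |

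4. **Enzalutamide.** If both drugs were held, Section 7.2 restarts it at 160 mg (160/160 = 100%). For toxicity of grade 3 or higher, Section 7.3.2 would instead reinstate it, if medically appropriate, at 120 mg (120/160 = 75%).

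5. **Who leaves this path before a restart.**
   - A patient whose elevation is due to progression is removed (Section 7.2.1.5).
   - A delay of more than 28 days ends participation (Section 7.2). The enzalutamide section allows only two weeks for grade 3 or 4 toxicity to resolve.
   - A patient already at 2 mg stops, because the second reduction in Table 2 is discontinuation.
   - A grade 4 event stops taselisib under the Table 3 catch-all.

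   A first event at 4 mg, below grade 4, that resolves in time meets none of these.

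6. **How many patients.** The frequency cannot be derived. Section 3.3.1.1 pools grades 3 and 4 and reports no concurrent bilirubin elevation. The planned phase II maximum in Section 15.4 is 37 + 12 = 49 (the same sentence also prints 59). That only bounds who could receive taselisib; it does not estimate how many would have the event. The number reaching taselisib may be lower, since crossover requires progression, qualifying laboratory values and agreement to a biopsy.

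**The case against.** The other side has real points. The event is rare, and the Table 1 rule is narrow: it needs the absence of any other explanation, in a population where liver metastases are allowed with AST/ALT up to 5 × ULN at entry. Phase Ib recorded no DLTs, with escalation to 8 mg, twice the phase II dose. Section 7 requires the cause to be evaluated, the values to fall, and follow-up at least weekly for 4 weeks after an interruption. Serious events go to the coordinating center within one business day, the safety committee reviews adverse events, and the investigator may withdraw any patient. The sponsor may also simply have preferred hold-and-reduce at 4 mg.

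Rarity stands, and so does the point that a restart is not automatic. But none of these measures bars the first re-challenge: they are conditions for restarting, after-the-fact review, or discretion. The clean phase Ib record covers cycle 1 in a small group. Section 7.2.1.3 shows its limits for another toxicity: no grade 3 or 4 rash in phase Ib, then 7 of 8 combination patients with grade 3 or 4 rash and fever in phase II at 4 mg. That says nothing about the liver, only that phase Ib tolerability did not carry over.

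One might add that phase Ib was not strict either, since after a DLT resolved "patients may be able to restart taselisib or enzalutamide at a lower dose at the discretion of the treating physician". That is a general permission. The combined rule is a specific permanent stop and is most naturally read as an exception to it.

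Three stronger readings are tempting and not supported:

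- **That grade 4 liver events are also unprotected in phase II**, because Section 7.2.1.5 does not itself cite Table 3. The opening line of Section 7.2 refers taselisib modifications to Table 3, and its catch-all stops taselisib at grade 4. That stop does not replace the combined rule, however: Table 1 lists "AST or ALT CTCAE Grade 4" as a separate criterion.
- **That the stop was once in Section 7 and was dropped.** The documents do not show this; an omission and a deliberate choice look the same on the page.
- **That phase Ib singled the event out because no other line in the hepatic row orders discontinuation.** That column defines DLTs, so the other lines would not be expected to order an action. The wording of the one line is what counts.

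**Conclusion.** The concern holds in a limited form. The combined stop is not carried into Section 7. For a first event at 4 mg taselisib that resolves within the permitted delay, is not due to progression and is below grade 4, Section 7 directs re-challenge at 2 mg where Table 1 would have given none. A return to 4 mg is possible only if both drugs were held, 28 days passed with good tolerance, and the physician chose it; it should not be read as the expected course. The conclusion assumes that normal in Section 7.2.1.5 means ULN and that Table 1 applies to phase Ib only, as its section and the completed status indicate. The event is expected to be rare, its frequency cannot be computed from the documents, and no efficacy result is affected.

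**What to change.** Add to Section 7.2.1.5 and to Table 3, stated to apply in phase II and crossover: *ALT/AST ≥ 3 × ULN with bilirubin > 2 × ULN and no explanation other than study drug: permanently discontinue study drug.* Except this event from the restart sentence in Section 7.2.1.5 and from the restart and 28-day re-escalation sentences in Section 7.2. The new line should say whether study drug means both agents; Table 1 does not define the term, although its hepatic follow-up column holds both.

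The cost is amendment wording. Transaminases and bilirubin are already in the scheduled laboratory panel, so no tests, visits or patients are added. The one drawback is that a rare patient loses the option of re-challenge. If the sponsor does intend to allow re-challenge after this event, the protocol should say so and give the reason.
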